8. STUDY PROCEDURES

See Table 5 below for the Schedule of Activities

Table 5 - Schedule of activities

Assessment	Screenin	Baseline	PON 1-3	POD 1-3	POD 3-7
	g	(1 hr)	(with	(15 min)	(15 min)
	(15 min)		bedtime		
			meds)		
Verbal consent	X				
CAGE-AID	X				
Written consent		X			
Demographics		X			
CCI		X			
Medication list		X			
Cognition/function					
TICS	X				
MoCA		Full, v8.1			
Lawton		X			
CDR		X			
WTAR		X			
Delirium					
3D-CAM	X			X	Χ [†]
DRS-R98				X	X [†]
Mental health					
PHQ-9		X			
GAD-7		X			
Sleep-related					
PSQI		X			
ESS		X			
RCSQ				X	X [†]
Medication administration			X		
AEs/SAEs					
Questionnaire		X		X	
Chart review*				X	X [†]
Subject to guess whether they received				POD 3	
daridorexant or placebo	 				

Abbreviations: **3D-CAM**, 3-Minute Diagnostic Interview for Confusion Assessment Method; **CAGE-AID**, CAGE [acronym for "Cut-down, Annoyed, Guilt, Eye-opener"] adapted to include drugs; **CCI**, Charlson comorbidity index; **CDR**, Clinical Dementia Rating; **DISH**, Depression Interview and Structured Hamilton; **DRS-R98**, Delirium Rating Scale, Revised 98; **ESS**, Epworth Sleepiness Scale; **GAD-7**, 7-item Generalized Anxiety Disorder scale; **Lawton**, Lawton Instrumental Activities of Daily Living; **MoCA**, Montreal Cognitive Assessment; **PHQ-9**, 9-item Patient Health Questionnaire; **POD**, postoperative day; **PON**, postoperative night (*i.e*, the night of POD 0 [the day of surgery] is defined as PON 1); **PSQI**, Pittsburgh Sleep Quality Index; **RCSQ**, Richards-Campbell Sleep Questionnaire; **TICS**, Telephone Interview for Cognitive Status; **WTAR**, Wechsler Test of Adult Reading

Screening procedures:

As indicated under **7. CONSENT PROCESS** above, consent will involve two steps—a verbal consent for study eligibility screening and, subsequently, signed consent. When obtaining verbal consent, we will

^{*}For evidence of adverse events, documentation of delirium, potential sleep confounds

[†]Daily assessments for delirium and sleep will continue if the subject is delirious on POD 3, until delirium resolves.

Version date: 2/3/2025

indicate to study prospects that the eligibility questions take 5–10 minutes. We indicate that we keep responses to screening questions, even for those who don't end up taking part, so, as a result and explain that we do not record personally identifying information during the screening process. Before proceeding with the remainder of the eligibility assessment, we also ask the prospective subject to affirm the availability of a study partner should they participate in the study.

Study duration:

Study subjects will participate from the initial screening evaluation prior to surgery, which is usually 1–2 weeks prior to scheduled surgery, through the third postoperative day after surgery (*note*: as in the following paragraph, assessments may be continued past POD 3 if the subject is found to have delirium on POD 3). Most subjects, then, will be enrolled in the study for roughly 2 weeks. However, the duration of study participation will be dependent on the scheduling of preoperative anesthesiology visit in relation to date of surgery.

Choice of POD and assessments for delirium:

We assess delirium on POD 1–3 with the DRS-R-98 as validated based on clinical interview under the supervision of a psychiatrist. We omit delirium assessment on POD 0 because (1) patients are intubated and sedated until the evening of POD 0 and (2) to exclude emergence delirium (*n.b.*, a distinct physiological event due to anesthetic effects¹⁰⁰). With one exception (see below), we restrict delirium assessments to POD 3 because (1) patients are often discharged on POD 3 or 4, (2) postop delirium peaks on POD 2 and 3, coincident with the peak of postop inflammation, ^{101,102} and (3) this allows a commensurate 3-day period across subjects to evaluate for delirium during the days of greatest risk. We use DRS-R-98 as it is well validated and the most robust tool for characterizing delirium phenomenology. ^{1,16,17,20,21,103} Regarding the exception referenced above: to determine delirium duration in all subjects, we continue to perform daily delirium assessments for any subject positive for delirium on POD 3 until no longer positive. Regardless of whether delirium assessments continue beyond POD 3, subjects will still receive study drug for only the first three nights after surgery.

Number of visits:

Subjects will have four (or up to a maximum of 8, if a person continues to score positive for delirium on POD 3 through POD 6) in-person visits with study personnel (see **Figure 1**, Timeline of Study Assessments in Section 4. STUDY DESIGN).

Blinding, including justification:

Blinding of study staff, clinical staff, and the patient is critical for this trial, which test whether daridorexant prevents postoperative delirium.

Justification of why subjects will not receive routine care or will have current therapy stopped:

Subjects will receive routine surgical and postoperative care. This trial adds exposure only to daridorexant or placebo to test whether daridorexant prevents delirium. No current therapy will be stopped or modified.

Justification for inclusion of a placebo group:

The use of a placebo treatment is essential to understand the effects (both positive and negative) of daridorexant exposure. Placebo comparison is the only way that we can understand what is likely due to daridorexant and what is not.

9. RISKS

Medical risks, listing all procedures, their major and minor risks and expected frequency

Below, **Table 6** lists the most common risks of daridorexant based on two pre-marketing studies.

Table 6 - Adverse events (AEs) and serious adverse events (SAEs) with daridorexant (DAR) and placebo⁵²

	Placebo	Placebo	DAR 50	DAR 25	DAR 25	DAR 10
	Study 1	Study 2	mg	mg	mg	mg
	n=309	n=306	Study 1	Study 2	Study 2	Study 2
			n=310	n=308	n=308	n=306
Any AE	105	100	116 (38%)	117 (38%)	121 (39%)	117 (38%)
	(34%)	(33%)				
Any SAE	7 (2%)	7 (2%)	3 (1%)	2 (1%)	3 (1%)	3 (1%)
Nasopharyngitis	20 (6%)	16 (5%)	20 (6%)	21 (7%)	13 (4%)	16 (5%)
Headache	12 (4%)	11 (4%)	19 (6%)	16 (5%)	15 (5%)	12 (4%)
Somnolence	6 (2%)	4 (1%)	5 (2%)	11 (4%)	10 (3%)	6 (2%)

The following three images are taken from the daridorexant package insert:

6.1 Clinical Trials Experience

Because clinical trials are conducted under widely varying conditions, adverse reaction rates observed in clinical trials of a drug cannot be directly compared to rates in clinical trials of another drug and may not reflect the rates observed in practice.

The safety of QUVIVIQ was evaluated in three placebo-controlled clinical studies (two 3-month studies of identical design [Study 1 and Study 2], and a 9-month extension study [Study 3]). Study 1 evaluated 50 mg and 25 mg doses of QUVIVIQ, while Study 2 evaluated a 25 mg dose and a 10 mg dose of QUVIVIQ. The 10 mg dose is not an approved dose. A total of 1232 patients (including approximately 40% elderly patients [\geqslant 65 years old]), received QUVIVIQ 50 mg (N = 308); 25 mg (N = 618); or 10 mg (an unapproved dose) (N = 306). A total of 576 patients were treated with QUVIVIQ for at least 6 months and 331 for at least 12 months.

Most Common Adverse Reactions

The most common reported adverse reaction (in at least 5% of patients and greater than placebo) during double-blind treatment in Study 1 was headache.

Table 1 shows adverse reactions that occurred in at least 2% of patients treated with QUVIVIQ and more frequently than in patients who received placebo in Study 1.

Table 1 Adverse Reactions Reported in $\geq 2\%$ of QUVIVIQ-treated Patients and Greater than in Placebo-treated Patients in a 3-Month Placebo-Controlled Study (Study 1)

	QUVIVIQ	QUVIVIQ	Placebo
	25 mg	50 mg	
	(N=310)	(N=308)	(N=309)
	%	%	%
Nervous System Disorders			
Headache ²	6	7	5
Somnolence or fatigue	6	5	4
Dizziness ⁻	2	3	2
Gastro-intestinal disorders			
Nausea [*]	0	3	2

^{*} The following terms were combined:

Headache includes: headache, tension headache, migraine, migraine with aura, head discomfort

Somnolence or fatigue includes: somnolence, sedation, fatigue, hypersomnia, lethargy

Dizziness includes: dizziness, vertigo, labyrinthitis Nausea includes: nausea, vomiting, procedural nausea

Other Adverse Reactions Observed During Clinical Trials (Study 1 and Study 2)

Other adverse reactions of < 2% frequency but greater than placebo are shown below. The following do not include adverse reactions 1) for which a drug cause was remote, 2) that were so general as to be uninformative, or 3) that were not considered to have clinically significant implications.

- Sleep paralysis was reported in 0.5% and 0.3% of patients receiving QUVIVIQ 25 mg and 50 mg, respectively, compared to no reports for placebo.
- Hypnagogic and hypnopompic hallucinations were reported in 0.6% of patients receiving QUVIVIQ 25 mg compared to no cases with QUVIVIQ 50 mg or placebo.

6.2 Post-Marketing Experience

The following adverse reactions have been identified during post-approval use of QUVIVIQ. Because these reactions are reported voluntarily from a population of uncertain size, it is not always possible to reliably estimate their frequency or establish a causal relationship to drug exposure.

Psychiatric disorders: Nightmares or abnormal dreams

Immune system disorders: Hypersensitivity (including angioedema, rash, urticaria)

Version date: 2/3/2025

Safety assessments:

In this trial, we obtain demographics and baseline assessment of medical morbidity, medications, cognitive status, and self-report sleep & mental health. Obtaining such information does not entail significant foreseeable risk beyond limited risk of psychological distress or questionnaire fatigue. As we will be completing the 9-question Patient Healthcare Questionnaire (PHQ-9), which assesses suicidal ideation, we have developed a safety plan for anyone who answers positively to question 9 on the PHQ-9 (see Steps taken to minimize risk below).

Adverse event definition:

This is an observational study of medically and surgically ill patients undergoing open-heart surgery, and this population—independent of this study—is at significant risk for a range of medical and surgical complications because of their underlying heart disease, open-heart surgery, and care provided during the perioperative period. In this study, we define an adverse event as any symptom, sign, illness, or experience that develops or worsens during the study that is reasonably attributable to the study assessments or receipt of daridorexant.

Serious adverse event:

A serious adverse event is defined as any adverse event resulting in any of the following:

- Sleep paralysis (inability to move or speak when going to sleep or waking up)
- Cataplexy (discrete episode of muscle weakness, typically associated with strong emotion)
- Complex behaviors while asleep that pose danger to the patient or others (e.g., sexually inappropriate acts)
- Angioedema or anaphylactic reaction to daridorexant
- Death/suicide
- Prolongation of existing hospitalization
- Persistent or significant disability or incapacity
- Medical or surgical intervention required to prevent permanent impairment or damage

Recording adverse events:

Each adverse event—whether observed by the PI or elicited from or volunteered by the subject—will be documented. Each adverse event will include a brief description of the experience, the date of onset, the date of resolution, the duration and type of experience, the severity, the nature of any potential relationship to study assessments, contributing factors, and any action taken with respect to the assessments. Any such adverse event will be reported to the Data and Safety Monitoring Advisory Council (see 16. Data and Safety Monitoring Plan).

Responsibilities for reporting serious adverse events:

The PI will record all serious adverse experiences that occur during the study period in the appropriate source documents and/or adverse events log as applicable. The timeframe for adverse event reporting will begin from the time of study enrollment to the final study assessment on POD 3 (or on a subsequent postoperative day for those with delirium on POD 3).

Steps taken to minimize risk:

We will adhere to the exclusion criteria listed above which will help avoid the recruitment of patients most at risk of side effects and adverse consequences. Patients will be interviewed each day for any side effects and the medical records will be reviewed and the data collected for Aim 4 of this study.

Risks pertaining to clinical assessment:

The risks pertaining to clinical assessment (neuropsychological testing and questionnaires) are anticipated to be no more than minimal. If the patient exhibits any distress or hesitation in answering specific

questions or completing a questionnaire in general, the evaluation will be suspended and the subject asked whether they wish to either take a break, skip a given section, or withdraw from the study. The PI [name] is a board-certified psychiatrist with clinical expertise in mental health evaluation. If he is conducting the assessment, he will use his medical judgment to determine whether to suspend evaluation or skip portions of the interview. If study personnel are conducting the evaluation, they will be instructed to contact [name] to join the interview and conduct additional assessment as necessary to determine whether the interview should be suspended or modified.

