1. PURPOSE OF THE STUDY

Purpose: This feasibility study is designed to inform and ultimately support a grant application for funding for an adequately powered randomized, clinical trial (RCT) of daridorexant to prevent postoperative delirium. In this phase 2 study, we will test the following specific aims:

Aim 1: To demonstrate that we can recruit subjects for a placebo-controlled RCT of daridorexant to prevent postoperative delirium.

Target: We will enroll up to 16 subjects. Our recruitment goal is four subjects per month, for a total of 12 subjects completing the protocol.

Aim 2: To demonstrate that we can deliver study compounds to subjects per our proposed methods, including successful use of the OnCore Enterprise Clinical Trial Management System. *Target*: All doses of study compound will be delivered successfully.

Aim 3: To demonstrate successful capture of preoperative, intraoperative, and postoperative data relevant for analyses during the conduct of this trial.

Target: We aim for 100% data capture, including subject retention through all doses of study compound.

Aim 4: To document all potential adverse events (AEs) and serious adverse events (SAEs). *Target*: All subjects will be evaluated daily after receipt of study compound for AEs and SAEs.

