4. STUDY DESIGN

This double-blind, parallel-group trial will randomize patients having cardiac surgery—either surgical aortic valve replacement (SAVR) or coronary artery bypass graft (CABG) surgery—to oral daridorexant 50 mg or identical-appearing placebo. The primary outcomes are feasibility and safety. Study subjects will provide written informed consent after receiving a complete description of the study. See Figure 1 below for a timeline of study assessments (not to scale).

[figure not shown]

Figure 1 – Timeline of Study Assessments

Abbreviations: 3D-CAM, 3-minute Diagnostic interview for the Confusion Assessment Method; CAGE-AID, CAGE [an acronym for "Cut down, Annoyed, Guilty, Eye-opener"] Adapted to Include Drugs; **POD**, postoperative day; **PON**, postoperative night; **TICS**, Telephone Interview for Cognitive Status *25 mg for subjects on a moderate 3A4 inhibitor (see 4.2 STUDY INTERVENTION below for details)

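### Section 9 counts an event as an AE, and hence as an SAE, only if it is judged attributable to the assessments or daridorexant, which narrows a primary safety outcome

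*Protocol*

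**What the plan says.** Section 9, under the adverse event definition, accepts an event as an AE only if it is one "that is reasonably attributable to the study assessments or receipt of daridorexant". The next paragraph builds on that: "A serious adverse event is defined as any adverse event resulting in any of the following". The list that follows includes death and a lengthened hospital stay. The definition opens with a reason: these patients face substantial medical and surgical complications whether or not they are in the study. That same opening states "This is an observational study of medically and surgically ill patients undergoing open-heart surgery".

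Other parts of the protocol bear on the same point:

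- Section 1, Aim 4: "To document all potential adverse events (AEs) and serious adverse events (SAEs".
- Section 4: "The primary outcomes are feasibility and safety".
- Section 9, on recording: each AE entry is to state "the nature of any potential relationship to study assessments, contributing factors, and any action taken with respect to the assessments".
- Section 9, on responsibilities: the PI records every serious adverse experience in the study period, and no attribution condition is attached.
- Section 16: the DSMB judges whether the nature, frequency and severity of AE reports fit expectations. Reporting to the review board depends on an AE being considered related to the study.

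**The concern.** Attribution works here as a condition of entry to the AE log, not as something recorded about an event already in it. Whether an event appears in the safety data then depends on a judgement about the individual patient, made in a population where other explanations are common. Three things are at stake. The first is the completeness of the AE and SAE counts that make up the safety part of the primary outcome. The second is the set of AE reports that the DSMB compares with expectations. The third is the use of these counts to plan the larger trial, which is the purpose of this study. In addition, the relationship and action fields quoted above name only the assessments, so an AE entry has no stated place for relationship to the drug under test.

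**Working it through.** No sample size, power or event figure in the protocol rests on this definition, so there is no planned figure to reproduce. The check is logical.

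**Step 1: what the definitions imply.**

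- AE = event AND attributable (Section 9, adverse event definition)
- SAE = AE AND listed outcome (Section 9, serious adverse event)
- So SAE = event AND attributable AND listed outcome

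A death on POD 2 that is judged surgical meets the outcome condition but not the attribution condition. It is neither an SAE nor an AE. The same holds for a prolonged stay.

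**Step 2: comparison with the rest of the protocol.**

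- *PI responsibilities (Section 9).* Serious adverse experiences are recorded without an attribution test. This is the most direct tension. The term is undefined, however, and may simply be another name for the SAEs defined just before it.
- *Relationship field (Section 9).* Relationship is asked of each AE. If attribution were already settled at entry, the field would be partly redundant, but asking about the nature of a link is compatible with having required one.
- *Review-board reporting (Section 16).* Relatedness is tested again. Under the Section 9 definition this is at most redundant.
- *Aim 4 (Section 1).* It covers potential events. The word may mean any event that might be adverse, or any event possibly attributable.

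The narrowing itself follows from the definitions alone. The conflicts with other sections depend on how those sections are read.

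**Step 3: what reduces the loss.** Section 9 provides daily interviews and record review. Table 5 schedules a questionnaire and chart review on POD 1–3. Section 16 lets the DSMB review the data collected. These govern what is found and who can see it. None clearly requires an event judged unattributable to be logged as an AE. Treating teams are asked to report potential events as the trial defines them, which leads back to the Section 9 definition.

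**Step 4: size.** Let N be the number of untoward events and u the share judged unattributable. Events left out of the AE count = N × u. The protocol gives neither N nor u, so the loss runs from none (u = 0) to every event judged surgical.

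**Step 5: postoperative days on which AEs are sought (workload, not loss).** On POD 1–3 this is 16 × 3 = 48 subject-days, or 12 × 3 = 36 for completers. Table 5 adds for later days: "Daily assessments for delirium and sleep will continue if the subject is delirious on POD 3, until delirium resolves". If every subject were followed to POD 7, the ceiling would be 16 × 7 = 112, or 12 × 7 = 84. That would need every subject to remain delirious through POD 6.

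**The case against.** The filter is deliberate and explained: Section 9 wants to keep background surgical complications out of the AE log. That stands as a reason, but a relationship field would separate background from related events without dropping any.

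A reader might infer that the protocol flatly contradicts itself. It does not go that far. Each of the other passages can be read to fit the definition, with some redundancy.

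A reader might also infer that any event with a surgical explanation is lost. The test is reasonable attribution, not sole or probable cause, and the AE record asks for contributing factors. An event with a surgical explanation can therefore still qualify.

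A third tempting inference is that placebo subjects can have no drug-attributable events, so that the arms cannot be compared. Section 8 requires study staff, clinical staff and patients to be blinded, so attribution is judged without knowledge of the arm and under the same rule in both.

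Finally, simply removing the attribution condition has effects elsewhere. Section 13 ties removal from the study to SAEs, and Section 9 has all AEs and SAEs reported as required. Incident delirium, the event the trial hopes to prevent, could become an AE. This objection stands in full, and the change must deal with it.

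**Conclusion.** The point holds as a weakness in a stated definition and should be fixed. Taken as written, Section 9 confines the AE and SAE counts, and the AE reports that the DSMB assesses, to events someone has attributed. That is too narrow for a drug trial with safety as a primary outcome. The effect on the between-arm comparison is that it covers fewer events, not that it is invalid. This assumes that attribution is made before any unblinding of the subject. The size of the loss is unknown, and existing ascertainment reduces it by an unknown amount. The tension with the recording rules, Section 16 and Aim 4 is largely by implication.

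Two drafting errors stand apart from this. The relationship and action fields omit the study compound, and a randomised, double-blind trial is called observational. Neither shows that the attribution filter is wrong, but both need correcting in the same text.

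**What to change.** In Section 9:

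- Log untoward events from enrollment to the final study assessment, whether or not considered related, identically in both arms. Define SAEs from that set.
- Record blinded relationship to the study compound and relationship to the assessments as separate fields, with action taken for each.
- Tabulate both all-cause and related events.
- State how incident delirium, which the trial already assesses, is handled in the AE log.
- Delete the description of the study as observational.

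The sponsor must also reconcile Section 13, where removal is tied to SAEs, and the reporting wording in Sections 9 and 16 with the new definition. Wider recording should not by itself change who is removed or what is reported.

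The cost is protocol wording, a revised AE form, more AE lines for at most 16 subjects, and realignment of those sections. No new contacts are needed: Table 5 already has a baseline questionnaire, a questionnaire and chart review on POD 1–3, and chart review afterwards if delirium persists. One limit remains. Table 5 schedules no AE contact between baseline and POD 1, so events in that interval would rest on recall and the chart. The length of the interval is not stated. The protocol times only the screening evaluation, "which is usually 1–2 weeks prior to scheduled surgery".

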5. INCLUSION

Inclusion criteria:

 \geq 60 yrs; having cardiac surgery at Strong Memorial Hospital; can provide consent; able to speak, read, and write English (as the instruments, including semi-structured interviews, used in this protocol have been validated in English); family member or close friend for collateral.

Exclusion criteria:

Exclusion criteria with rationales are described in **Table 4**. Subjects will be screened in person or by phone for eligibility.

Table 4 - Exclusion criteria with explanation				
Exclusion criteria	Definition (rationale)			
Prior cardiotomy	Per self-report or chart (sequelae of prior surgery)			
Infectious endocarditis	Per chart (potential septic emboli)			
Emergency surgery	Per chart (baseline eval impossible)			
Delirium at baseline	Positive 3D-CAM (limit to incident delirium)			
Auditory/visual impairment prevents study procedures	Per self-report or demonstrated inability during baseline visit (inability to participate)			
Alcohol/substance misuse	CAGE-AID score of 2 or greater (exclude cognitive effects of substances)			
Psychotic disorder	Per self-report or chart (can confound delirium assessment)			
Dementia-level deficits	Per self-report, chart, or TICS < 27 (exclude effects of dementia on delirium assessments)			
Use of a sleep aid	Any prescribed sleep aid being taken at least every other night (potential confound)			
Use of a strong 3A4 inhibitor (per FDA website ⁹²)	Ceritinib, clarithromycin, cobicistat, idelalisib, itraconazole, ketoconazole, nefazodone, nelfinavir, posaconazole, ritonavir, telithromycin, voriconazole (increases drug exposure)			
Intolerance to daridorexant	Per self-report or chart (safety)			
Severe kidney or liver impairment	Child-Pugh score ≥ 7, Cockcroft-Gault < 30 mL/min, or current dialysis (safety)			
Narcolepsy	Per self-report or chart (daridorexant is contraindicated in narcolepsy)			
Prior suicide attempt	Per self-report or chart (package insert indicates a risk of worsening depression or suicidality)			
Suicidal ideation at baseline assessment	Per self-report (package insert indicates a risk of worsening depression or suicidality)			
Any condition that in th study	e opinion of the PI compromises patient safety or data quality if enrolled in the			

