
Plan for breaking the blind for a subject

If a patient has a medical emergency that requires immediate clinical care for stabilization, including angioedema, anaphylaxis, attempted suicide, or any other condition that is considered—in the opinion of the PI or the primary medical team—as potentially attributable to daridorexant, we will contact the IDS pharmacist to identify whether the patient has received daridorexant or placebo. If this occurs, the subject will be withdrawn from the study, and this will be reported to the RSRB and DSMB.

Legal risks such as the risks that would be associated with breach of confidentiality:

As with any study incorporating research into clinical care, there is a small but real risk of unintentional release of HPI. We will make every effort to secure data and study records under double lock/key and encryption in keeping with institutional standards to prevent this from occurring.

Version date: 2/3/2025

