13. SUBJECT WITHDRAWALS

Definition of treatment failure or subject removal criteria:

All consented subjects will be retained in the study, and all primary analyses will be performed per protocol. All daridorexant arm subjects who develop postop delirium represent patients for whom daridorexant failed to prevent delirium. However, we do not expect daridorexant to prevent all delirium, so we would not use the term "treatment failure" to describe incident delirium in these patients. We would remove patients from the study only in the event of serious adverse events.

What happens to subjects when study ends or if a subject's participation in the study ends prematurely:

Patients will be thanked for their participation in the study and will be advised to call the PI with any questions. Study agent—either daridorexant or placebo—is being provided for up to the first three nights after surgery, but we will not be providing this to those who discharge prior to this. Early discharges are not only rare but indicate that the patient is doing so well that they no longer require inpatient level of care, which implies that they would not have delirium at the time.

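### The SAE list leaves out attempted suicide and life-threatening events, which the emergency-unblinding rule covers, and the withdrawal rules conflict when an unblinded event is not an SAE

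*Protocol*

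**What the plan says.** **SAE definition (Protocol Section 9, Serious adverse event).** The lead-in is "A serious adverse event is defined as any adverse event resulting in any of the following". Eight entries follow:

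- three sleep-related events (sleep paralysis, cataplexy, dangerous behaviours during sleep);
- "Angioedema or anaphylactic reaction to daridorexant";
- "Death/suicide";
- "Prolongation of existing hospitalization";
- lasting or significant disability;
- "Medical or surgical intervention required to prevent permanent impairment or damage".

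**Emergency unblinding (Section 9, Plan for breaking the blind).** In an emergency needing immediate stabilising care, "including angioedema, anaphylaxis, attempted suicide, or any other condition" that the investigator or treating team thinks potentially due to daridorexant, the pharmacist discloses the allocation. The subject is then withdrawn, and the RSRB and DSMB are told.

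**Removal (Section 13).** "We would remove patients from the study only in the event of serious adverse events".

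**Suicidality as a drug risk (Section 5, Table 4).** Two exclusion criteria, a past attempt and ideation at baseline, carry the rationale "package insert indicates a risk of worsening depression or suicidality". In the schedule of activities (Section 8, Table 5) the PHQ-9 is marked at baseline only. An AE/SAE questionnaire and a chart review are marked for POD 1–3.

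**The concern.** Two parts of Section 9 describe the same kind of event, an acute emergency that may be due to the drug, but do not draw the boundary in the same place. The unblinding rule treats attempted suicide as grave enough to break the blind. The SAE list does not name it and has no life-threatening item to take its place.

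Three things depend on that boundary. Section 4 makes safety a primary outcome alongside feasibility, and Aim 4 is to document AEs and SAEs, so the list decides what enters the SAE tally. Section 9 asks treating teams to report events according to the trial's own definitions, so the list is a working instruction. Section 13 makes removal depend on SAE status, so a gap in the list becomes a contradiction about who leaves the study. That bears on Aim 3, which targets complete retention through all doses.

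**Working it through.** The protocol gives no figure to reproduce. The check sets the definitions side by side and then reads Table 5.

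**Step 1. Unblinding triggers against the SAE list**

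| Trigger in the unblinding rule | Named in the SAE list? | Other route to SAE status |
|---|---|---|
| Angioedema | Yes | not needed |
| Anaphylaxis | Yes | not needed |
| Attempted suicide | No; the suicide entry is paired with death | longer stay, disability, or intervention to avert permanent damage |
| Any other potentially attributable emergency | No general life-threatening item | the same routes, or death, or if it is one of the named sleep events |

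Named triggers on the list: 2 of 3. The open category has no direct counterpart.

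**Step 2. What falls through.** Take a non-fatal attempt, or another emergency outside the named entries, that is stabilised. Suppose the stay is not lengthened, no disability follows, and the care given was not needed to avert permanent damage. It meets the unblinding rule and none of the eight entries. If judged attributable to the drug, it is recorded as an adverse event but not as a serious one.

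**Step 3. Withdrawal.** For the event in Step 2:

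- unblinding rule: subject withdrawn;
- Section 13: removal for SAEs only, and this is not one.

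Both cannot be followed. For an unblinded event that is an SAE, the two statements agree.

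**Step 4. Effect of one label.** Section 4.1 plans 16 enrolled and 12 completing. One event classed differently moves the overall proportion of subjects with an SAE by 1/16 = 6.25 percentage points (all enrolled) or 1/12 = 8.3 points (completers). This is the effect if such an event occurs. The protocol gives no rate from which to judge how likely that is.

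**Step 5. Suicidality after dosing.** The PHQ-9 is the only scheduled instrument that the protocol says assesses suicidal ideation. Table 5 marks it at baseline and on 0 of the 3 days POD 1–3. The general AE/SAE questionnaire is marked for POD 1–3, but its content is not given.

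**The case against.** The strongest reply is that the list already has broad entries. "Medical or surgical intervention required to prevent permanent impairment or damage" depends on what the intervention was meant to prevent, not on whether harm followed, so successful treatment does not by itself take an event off the list. An emergency needing stabilisation will often meet that entry or "Prolongation of existing hospitalization". This stands, and it narrows the gap to the residual case in Step 2. It does not close it, because immediate care can be needed where permanent damage is not in prospect.

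Oversight also does not depend on the label. Section 9 sends AEs as well as SAEs to the RSRB and DSMB, and reports any unblinding separately. That stands too: what can go wrong is the classification and the tally, not whether the DSMB hears of the event.

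A reader might infer that an attempt could pass unnoticed. The protocol does not support this. Dosed subjects are postoperative inpatients with daily side-effect interviews, record review and reporting by the treating team. A reader might also infer that suicidality is not assessed at all after dosing. That cannot be shown either, because the questionnaire may ask about it. The realistic gap is ideation that a subject does not volunteer. The protocol also reduces the risk at entry through its two exclusions, and it expects acute suicidality to be very rare.

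Nor does the protocol rank these emergencies as the ones most likely caused by the drug. It calls them only potentially attributable.

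**Conclusion.** The mismatch is real but limited. One of three named unblinding triggers is missing from the SAE list, and the open category of emergencies has no life-threatening item behind it. An event in the gap would reach the RSRB and DSMB but would count as non-serious. For that same event, Sections 9 and 13 give incompatible instructions on withdrawal.

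This rests on three readings: that the entry "Death/suicide" does not extend to a non-fatal attempt; that the event is judged attributable enough to be an adverse event under Section 9; and that none of the general outcomes applies to it. The chance of such an event in this small study is low, but the text is easily corrected and the study is meant to inform a larger trial.

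The secondary point is weaker. No suicidality-specific measure is named for the days after dosing, although the protocol cites suicidality as a labelled risk. Whether the questionnaire fills that gap is unknown from the document.

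**What to change.** 1. In Section 9, add attempted suicide and life-threatening events to the SAE list so that it covers the unblinding triggers. This keeps seriousness tied to the nature of the event rather than to whether the pharmacist was called.
2. Reconcile the withdrawal statement in the unblinding plan with the removal rule in Section 13. Which rule should apply is for the study team to decide. This is needed even after the first change, because an emergency could still lead to unblinding without meeting any SAE entry.
3. Confirm that the existing POD 1–3 AE questionnaire asks about suicidality, or add one question to it. The safety plan for a positive PHQ-9 item 9 could serve for positive answers.

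**Cost:** a short edit to the list, one reconciled statement on withdrawal and, at most, one question at each of three visits already planned. SAE counts may be slightly higher.
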